5. STUDY DESIGN

This is an open-label, multicenter, Phase II study to be conducted in 2 stages. All patients will receive orteronel PO at a dose of 300 mg twice daily (BID) (600 mg total daily dose).

- Lead-in Phase: The first 6 patients treated will be evaluated every week to confirm the safety and feasibility of this regimen. After all 6 patients complete at least 4 weeks of treatment, and if no prohibitive toxicities are identified, continuous study treatment will begin.
- Continuous Study Treatment: Patients will continue to be enrolled into both cohorts based on their tumor specificities up to a total of 31 patients in Cohort 1 (ER-/PR-/HER2-/AR+) and 55 patients in Cohort 2 (ER+ and/or PR+/AR+). These numbers include the patients that are participating in the lead-in phase.

Up to 86 patients are planned to be enrolled in this study (6 for the lead-in phase and 80 for continuous study treatment).

Patients will be evaluated every eight weeks for response to treatment.

All patients who respond to treatment (complete response [CR] or partial response [PR]) or have stable disease (SD) will continue to receive orteronel until they develop progressive disease (PD) or unacceptable toxicity.

The study design schema is presented in Figure 1.

[figure not shown]
CONFIDENTIAL

STUDY DRUG: Orteronel

SCRI INNOVATIONS STUDY NUMBER: BRE 203

DATE OF PROTOCOL: Version 3.0 30 October 2013

Figure 1. BRE 203 Treatment Schema

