7.5. End of Study Treatment

Patients are permitted to continue treatment with orteronel until disease progression, or the patient is discontinued due to unacceptable toxicity or a decision to discontinue treatment by the patient or the study physician. Patients will return to the study center \leq 30 days after treatment ends for the following assessments:

- Update of medical history
- Physical examination including measurement of weight and vital signs
- ECOG performance status
- AE assessment
- Concomitant medication review
- Study drug compliance assessment
- CBC, including 3-part differential and platelets
- CMP
- Fasting plasma glucose, insulin, c-peptide, and HbA_{1c} (only in patients with a history of diabetes)
- Serum hormone levels: estradiol, total and free testosterone, SHBG, ACTH, DHEA-S, and cortisol

CONFIDENTIAL

STUDY DRUG: Orteronel

SCRI INNOVATIONS STUDY NUMBER: BRE 203

DATE OF PROTOCOL: Version 3.0 30 October 2013

- Serum amylase/lipase
- Urinalysis
- CT scan of the chest /abdomen/pelvis, if no documented progressive disease and the last assessment was >8 weeks prior (only those scans abnormal at baseline need to be repeated)

If treatment is discontinued because of toxicity or any other reason(s) at a treatment visit and no study treatment is administered, that visit may fulfill the End-of-Treatment Visit.

After withdrawal from protocol treatment, patients must be followed for AEs for 30 calendar days after the last dose of study drug.

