7.6. Follow-Up

7.6.1. Follow-Up After Discontinuing Study Treatment

Patients discontinuing treatment for any reason other than progressive disease will be monitored for evidence of disease progression. Disease progression will be assessed every 6 months for 2 years and annually thereafter, up to a maximum of 5 years after the last patient has enrolled on the study. Imaging scans will be done as clinically indicated for evaluation of any new symptoms and assessment for disease progression. After disease progression is documented, patients will be followed as specified in Section 7.6.2.

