10.6. Efficacy Measures

The primary efficacy endpoints for both Cohort 1 and Cohort 2 are the RR and DCR.

Secondary efficacy endpoints are PFS and OS.

Efficacy analyses will include all patients in the ITT population.

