10.6.2. Secondary Endpoints

Progression-free survival (PFS) and OS will be analyzed using Kaplan-Meier methods. Each of these endpoints will be presented graphically and further reported using the respective median time point estimate along with its 95% CI.

PFS will be measured from the date of first protocol treatment until the date of objective disease progression or date of death is documented (event), or date of last adequate tumor assessment (censored). If a patient receives non-protocol therapy for the study indication prior to incurring an event, the earliest date of non-protocol treatment recorded will be used (censored). If no post-treatment tumor assessment has been performed, PFS for the patient will be censored at time zero.

OS will be measured from the date of first protocol treatment until the date of death is documented (event), or date last known alive (censored). If a patient receives non-protocol therapy for the study indication prior to incurring an event, the earliest date of non-protocol treatment recorded will be used (censored).

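### PFS is censored at the start of non-protocol therapy rather than at the last tumor assessment, so time without a tumor assessment can count as progression-free

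*Combined protocol and SAP*

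**What the plan says.** Section 10.6.2 gives three censoring dates for PFS:

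- An event-free patient is censored at the last adequate assessment: "or date of last adequate tumor assessment (censored").
- If non-protocol therapy for the study indication comes before an event, "the earliest date of non-protocol treatment recorded will be used (censored").
- For a patient never assessed: "If no post-treatment tumor assessment has been performed, PFS for the patient will be censored at time zero".

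No order of precedence is given between the second and third.

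The visit schedule determines how much is seen before new therapy starts. On treatment, Section 5 says: "Patients will be evaluated every eight weeks for response to treatment". At end of treatment, Section 7.5 asks for a CT only "if no documented progressive disease and the last assessment was >8 weeks prior". For patients who stop without progression, Section 7.6.1 says: "Disease progression will be assessed every 6 months for 2 years and annually thereafter", with imaging as clinically indicated.

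On the role of the endpoint, Section 10.6 says: "Secondary efficacy endpoints are PFS and OS". Section 10.6.2 adds: "Progression-free survival (PFS) and OS will be analyzed using Kaplan-Meier methods", reported as a curve and a median with its 95% CI.

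**The concern.** The default date recognizes that a patient is known to be progression-free only up to the last adequate assessment. The exception for new therapy drops that principle and keeps the patient in the risk set until a date that need not coincide with any assessment.

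The schedule leaves room for such a gap. A patient who stops within 8 weeks of the last scan has no end-of-treatment CT, and the next planned progression check may be 6 months away. Section 3.3 lists several reasons for stopping other than progression, including toxicity and patient request, so such patients can be expected.

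At stake is the PFS curve and its median in each cohort. There is no control arm in which the same effect could offset it.

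**Working it through.** **Plan's own figure.** There is none to reproduce. The documents give no assumed PFS median, event count, switching rate or PFS hypothesis.

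**Direction.** Compare the stated rule with censoring at the last adequate assessment on or before the new therapy.

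1. Only a censoring date changes, so both rules have the same events at the same times.
2. The Kaplan-Meier estimate is S(t) = ∏(1 − d/n) over event times up to t, where d is the number of events and n the number at risk.
3. The therapy start is never earlier than the assessment it replaces. At each event time the stated rule therefore has n + k at risk, with k ≥ 0 switchers still counted.
4. Since 1 − d/(n + k) ≥ 1 − d/n, the stated curve is never lower. It is strictly higher from the first time another patient's event falls inside a switcher's gap.

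A check on 2,000 simulated trials found no violation. With fixed visits, no between-visit events and the gap inside one scan interval, the two curves coincided.

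**Size, first set of assumptions.** None of these come from the documents except the 8-week interval: exponential PFS, exact 8-weekly scans, stopping independent of progression, new therapy 2 to 8 weeks after stopping. True PFS at 16 weeks (112 days) is 2^(−112/60) = 27.4% for a 60-day median and 2^(−112/90) = 42.2% for a 90-day median.

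| True median | Censored at new therapy | True 16-week PFS | Stated rule, time-zero rule not applied | Stated rule, time-zero rule applied |
|---|---|---|---|---|
| 60 days | 28% | 27.4% | 32.7% (+5.3) | 30.0% (+2.6) |
| 60 days | 40% | 27.4% | 36.1% (+8.7) | 31.5% (+4.1) |
| 90 days | 19% | 42.2% | 44% (about +2) | 43.3% (+1.1) |

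In the 28% scenario, censoring at the last scan gave 27.4%. In the 40% scenario, 60% of the patients censored this way had never been scanned, which is why the time-zero rule matters so much. With 11-14% censored the excess is about 1 to 2 points; with 6-10% it is about 0.4 to 1.2 points.

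**Size, second set of assumptions.** 50 patients (the Cohort 2 evaluable number), 400 replicates per cell, 8-weekly scans with ±5 days of jitter, 20% of progressions or deaths seen between scans, median 9, 16 or 26 weeks, and 10%, 20% or 30% stopping before documented progression. The reference is the same patients scanned 8-weekly without switching.

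| Stopping to new therapy | Excess in 26-week PFS (points), time-zero rule not applied | Time-zero rule applied |
|---|---|---|
| 2 weeks | 0 to 1.5 | 0 to 0.7 |
| 8 weeks | 0.7 to 8.6 | 0.3 to 4.6 |
| 24 weeks | 1.6 to 22.3 | 0.5 to 8.2 |

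Here last-assessment censoring erred the other way, by 0.4 to 4.2 points.

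**The case against.** Five points can be made for the plan.

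- **The time-zero sentence.** Read literally, it gives no credit to a patient who switches before any scan, and in the scenarios above it roughly halves the excess. This stands. Because precedence is not stated, both readings have to be shown. An excess remains under either, except at very short gaps.
- **The gap is not wholly unmonitored.** A reader might infer from Section 7.6.1 alone that nobody looks. Sections 7.5 and 7.6.1 do not support that: there is a conditional end-of-treatment CT, symptoms can prompt imaging, and deaths still count as events. With the CT modeled at an assumed 0 to 30 days after stopping, the 36.1% figure falls to 33.9%. The gap is reduced, not closed.
- **Switching may be rare.** Treatment continues to progression or unacceptable toxicity, and Section 6.1 expects the drug to be well tolerated. Nothing in the documents supports 20-40% switching without progression. This stands, and at low rates the effect is small.
- **The last-scan date is not exact either.** A reader might infer that it recovers the true curve. It does so with fixed visits and independent stopping, but not with jittered visits and between-scan events.
- **PFS decides nothing.** This also stands. There is no PFS test or PFS benchmark; the exemestane figures in Section 10.3 are response and clinical benefit rates.

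**Conclusion.** The rule is wrong as written, with a modest consequence. Its direction relative to the plan's own default is certain: the PFS curve is never lower and is usually higher.

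The size rests on assumptions the documents do not supply. Under the first set, with a median of 60 to 90 days, the overstatement of 16-week PFS is about 1 to 2 points at 11-14% censored this way and about 2 to 5 points at 28-34%. The lower ends apply if the time-zero rule takes precedence. The effect is near nil when new therapy follows a scan promptly and larger when the unimaged gap is long.

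A reader might go further and infer that the trial's conclusions about activity are compromised. The documents do not support that. The stopping and success rules in Section 10.4 count responses, and response rate and disease control rate in Section 10.6.1 do not use the PFS censoring date.

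**What to change.** In Section 10.6.2, replace the PFS sentence on non-protocol therapy with: *If non-protocol therapy starts before an event, PFS is censored at the last adequate tumor assessment on or before the start of that therapy, or at time zero if there is none.* This also settles the precedence question for patients never assessed.

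Add a sensitivity analysis that ignores the start of new therapy and uses progression and death whenever recorded. It is needed because neither censoring date removes the informative censoring that arises when patients switch at impending progression. Its progression dates will be coarse, given the 6-monthly checks in Section 7.6.1.

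The cost is a wording change and one extra analysis, with no added patients, visits or scans. The PFS estimate may be slightly less favorable. The change concerns PFS only; the parallel sentence for OS is a separate question.

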 - Alanine aminotransferase (ALT) and aspartate aminotransferase (AST) $\leq 2.5 \times$ the upper limit of normal (ULN), if no liver involvement or $\leq 5 \times$ ULN with liver involvement
 - Total bilirubin ≤ 1.5 times the upper limit of normal (ULN) (in patients with known Gilbert Syndrome, a total bilirubin $\leq 3.0 \times$ ULN, with direct bilirubin $\leq 1.5 \times$ ULN)
10. Adequate renal function, defined as:
 - Creatinine $\leq 1.5 \times$ ULN or creatinine clearance $\geq 40 \text{ mL/min}$, as calculated by the Cockcroft-Gault method
11. Screening calculated LVEF of $\geq 50\%$ by echocardiogram (ECHO) or by multiple-gated acquisition (MUGA) scan
12. Ability to swallow and retain oral medication
13. Male patients, even post vasectomy, who are willing to use adequate contraceptive measures (see Appendix B) or abstain from heterosexual intercourse during the entire study treatment period and for 4 months after the last dose of study drug
14. Female patients who are not of child-bearing potential and female patients of child-bearing potential who agree to use adequate contraceptive measures (see Appendix B) or abstain from heterosexual intercourse during the entire study treatment period and for 4 months after the last dose of study drug, who are not breastfeeding, and who have had a negative serum/urine pregnancy test ≤ 7 days prior to dosing
15. Life expectancy of ≥ 3 months
16. Willingness and ability to understand the nature of this study and to comply with the study and follow-up procedures.

CONFIDENTIAL

STUDY DRUG: Orteronel

SCRI INNOVATIONS STUDY NUMBER: BRE 203

DATE OF PROTOCOL: Version 3.0 30 October 2013

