7.4. Treatment Assessments

Study treatment will be given in 4-week (28-day) cycles (± 5 days) for all patients.

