7.4.1. Day 1 of Each Cycle

The following assessments will be performed on Day 1 of each cycle:

- Medical history
- Physical examination including measurements of weight and vital signs (resting heart rate, blood pressure, respiratory rate, and oral temperature) (**weekly during Cycle 1 for Lead-in patients**)
- ECOG performance status
- AE assessment (**weekly during Cycle 1 for Lead-in patients**)
- Concomitant medication review (**weekly during Cycle 1 for Lead-in patients**)
- CBC, including 3-part differential and platelets (Day 1 of each cycle ± 3 days) (**weekly during Cycle 1 for Lead-in patients**)(need not be done on Cycle 1 Day 1 if baseline was taken within 72 hours of that day)

CONFIDENTIAL

STUDY DRUG: Orteronel

SCRI INNOVATIONS STUDY NUMBER: BRE 203

DATE OF PROTOCOL: Version 3.0 30 October 2013

- CMP (Day 1 of each cycle \pm 3 days) (**weekly during Cycle 1 for Lead-in patients**) (need not be done on Cycle 1 Day 1 if baseline was taken within 72 hours of that day)
- Serum hormone levels: estradiol, total and free testosterone, SHBG, ACTH, DHEA-S, and cortisol (**Day 1 of Cycles 2, 4 and End of Treatment only** [see Section 7.5])
- Serum amylase/lipase
- Serum/urine pregnancy test (for women of childbearing potential only). If the baseline reading was done within 72 hours of Cycle 1 Day 1, this test need not be repeated on that day.
- Study drug compliance assessment

7.4.2. Day 1 of Cycle 3 and Every Other Cycle Following (Cycles 5, 7, 9, etc), except where noted

- Fasting plasma glucose, insulin, c-peptide, and HbA_{1c} (only in patients with a history of diabetes)
- 12-lead ECG
- CT scan of the chest /abdomen/pelvis (only those scans abnormal at baseline need to be repeated)
- Bone scan (if clinically indicated)
- CT/MRI of the brain (if clinically indicated)

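### The PFS definition does not say whether a death before any post-baseline scan is an event or is censored at time zero

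*Combined protocol and SAP*

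**What the plan says.** The PFS paragraph of Section 10.6.2 has three parts.

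- The opening sentence runs PFS from first protocol treatment "until the date of objective disease progression or date of death is documented (event), or date of last adequate tumor assessment (censored". Death is an event, and no scan is required beforehand.
- The next sentence deals with patients who take non-protocol therapy "prior to incurring an event, the earliest date of non-protocol treatment recorded will be used (censored". It carries its own limit: it applies only where no event has yet occurred.
- The closing sentence reads "If no post-treatment tumor assessment has been performed, PFS for the patient will be censored at time zero". It carries no such limit and makes no exception for death.

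On timing, Section 5 states "Patients will be evaluated every eight weeks for response to treatment". Section 7.4 states "Study treatment will be given in 4-week (28-day) cycles (± 5 days) for all patients", and the CT scans are listed in Section 7.4.2 under "Day 1 of Cycle 3 and Every Other Cycle Following (Cycles 5, 7, 9, etc". The first scheduled on-treatment scan therefore falls at about week 8. Section 10.6 puts all efficacy analyses on the ITT population, so early deaths stay in the PFS analysis. PFS is reported as a Kaplan-Meier curve and a median with 95% CI.

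**The concern.** A patient who dies before the first on-treatment scan meets the event condition of the opening sentence and the time-zero condition of the closing one. No section gives precedence. Two programmers could each follow the text and produce different curves from the same data.

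The two codings are not equivalent. Censoring at time zero removes the patient from every risk set, so the patients who fail soonest no longer count as failures. The error can go only one way, towards a better-looking curve. If the choice is left until such deaths are known, in an open-label trial, it is no longer pre-specified.

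**Working it through.** The documents give no PFS assumption, event count or median, so there is no stated figure to reproduce. The check has a textual part and a numerical part.

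**Text.** Take a patient who dies at week 4 with only a baseline scan.

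- Opening sentence: event at week 4.
- Non-protocol-therapy sentence: does not apply.
- Closing sentence, read literally: censored at time zero.

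I read post-treatment in the closing sentence as meaning after the start of treatment, which is the only sensible sense.

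**Exact effect.** Inputs: n = 31 and n = 55, the planned cohort sizes in Section 5. The number k of unscanned deaths is assumed, because the documents do not give it. Suppose the k deaths precede every other event or censoring.

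- Coded as events, the curve after the last of them is (n-k)/n, and later S(t) = ((n-k)/n) × S_rest(t).
- Coded as censored at zero, the later curve is S_rest(t).
- S_rest is the same in both, because the later risk sets hold the same n-k patients. The ratio is therefore n/(n-k) at every later time, with no assumption about the shape of PFS.

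| n | k | Just before first scan, deaths as events | Censored at zero | Multiplier on later curve |
|---|---|---|---|---|
| 31 | 1 | 30/31 = 96.8% | 100% | 1.033 |
| 31 | 3 | 28/31 = 90.3% | 100% | 1.107 |
| 31 | 5 | 26/31 = 83.9% | 100% | 1.192 |
| 55 | 1 | 54/55 = 98.2% | 100% | 1.019 |
| 55 | 5 | 50/55 = 90.9% | 100% | 1.100 |
| 55 | 8 | 47/55 = 85.5% | 100% | 1.170 |

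**Worked example past the first scan.** Assumed: deaths at week 4, and about 45% of patients still progression-free progress at each 8-weekly scan.

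- n = 31, k = 2: 29 patients are scanned at week 8, 13 progress and 16 remain. Week-8 PFS is 16/31 = 51.6% against 16/29 = 55.2%. The median is week 16 under both.
- n = 31, k = 3: 28 are scanned, 13 progress and 15 remain. Week-8 PFS is 15/31 = 48.4% against 15/28 = 53.6%. The median is week 8 against week 16.
- n = 55, k = 3: 52 are scanned, 23 progress and 29 remain. Week-8 PFS is 29/55 = 52.7% against 29/52 = 55.8%. The median is week 16 under both.
- n = 55, k = 6: 49 are scanned, 22 progress and 27 remain. Week-8 PFS is 27/55 = 49.1% against 27/49 = 55.1%. The median is week 8 against week 16.

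**How often the median moves.** Simulation, 10,000 trials per setting. Assumed: deaths uniform over days 7 to 48; exponential progression in the rest with latent median 2 to 4 months, found at the next 8-weekly scan; scan dates shifted by up to 5 days; no other censoring. Share of trials in which the literal reading raises the median by 6 weeks or more, in effect one scan interval:

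- n = 31: 0% for one death, 14-20% for three, 30-41% for five.
- n = 55: 0% for one death, 12-25% for five, 29-50% for eight.

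**The case against.** The strongest reply is that the paragraph can be read without conflict. The opening sentence has an event limb and a censoring limb, and the closing sentence supplies the censoring date when no adequate assessment exists. A patient who has died already has an event and never reaches the censoring limb. Many programmers would code it that way, and there would then be no bias. This is plausible, and for that reason the point is an ambiguity and not a demonstrated bias. It does not dispose of the point: the preceding sentence states that it applies only before an event, and the closing one does not.

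Second, such deaths may be few. Section 3.1 requires "Life expectancy of ≥ 3 months", and Section 7.5 asks for a CT at the end-of-treatment visit when there is no documented progression and the last assessment is more than 8 weeks old. Both reduce the number, but neither makes it zero. Section 3.1 admits ECOG 2, and a patient scanned 1 week before dosing who stops at week 3 and attends at week 4 is only 5 weeks from the last scan, so no CT is due. After that, Section 7.6.1 provides "Disease progression will be assessed every 6 months for 2 years and annually thereafter", with imaging only when clinically indicated. A death some months later could still be unscanned, although the n/(n-k) factor would not then hold exactly.

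A reader might also infer that the non-protocol-therapy rule is an error because it credits unscanned time up to the therapy date. The documents do not support that. The rule is explicit and can be programmed as written; it is a choice of convention. Any estimate of its effect would also have to allow for the end-of-treatment CT.

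**Conclusion.** The point stands as an ambiguity in a stated rule that, followed literally, biases PFS upward. The factor n/(n-k) is exact when the k deaths precede every other event or censoring. The week-8 and median results rest on the assumed values of k and progression rates shown above.

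Three stronger conclusions are tempting but not supported:

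- That the planned PFS analysis is biased. It is not if the opening sentence governs.
- That the reported median will be inflated. The number of unscanned deaths cannot be found from the documents, and with one such death no simulated trial moved by 6 weeks or more. The larger shares need several early deaths.
- That the trial's conclusion is at risk. PFS is secondary and descriptive, with no hypothesis attached. The stopping and success rules in Sections 10.3 and 10.4 use response counts only.

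The correction should nevertheless be made before PFS is analysed.

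**What to change.** Replace the closing sentence of the PFS paragraph in Section 10.6.2 with:

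> *A patient who has no post-baseline tumor assessment and has not died is censored for PFS at Day 1. A death without a post-baseline assessment, and before any non-protocol therapy, is a PFS event on the date of death.*

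This follows the plan's own opening sentence. It leaves one limit: an unscanned patient who dies long after stopping is credited with PFS up to death.

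The cost is one sentence, with no new data and no change to sample size or decision rules. Compared with the literal reading, PFS changes only if a patient dies without a post-baseline scan and before any non-protocol therapy. No change to the non-protocol-therapy rule, and no added sensitivity analysis of it, is required on this point.

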7.6.2. Follow-Up After Disease Progression

After disease progression is documented, survival will be monitored every 6 months for 2 years and annually thereafter, up to a maximum of 5 years after the last patient has enrolled on the study. Patients may be contacted during outpatient visits or by telephone.

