- ⁿ All patients will undergo the end-of-treatment assessments listed within 30 days after treatment ends. Patients must be followed for AEs for 30 calendar days after the last dose of study drug.
- ^o Patients discontinuing treatment for any reason other than progressive disease will be monitored for evidence of disease progression. Disease progression will be assessed every 6 months for 2 years and annually thereafter, up to a maximum of 5 years after the last patient has enrolled on the study. Imaging scans will be done as clinically indicated for evaluation of any new symptoms and assessment for disease progression.
- ^p After disease progression is documented, survival will be monitored every 6 months for 2 years and annually thereafter, up to a maximum of 5 years after the last patient has enrolled on the study. Patients may be contacted during outpatient visits or by telephone.

CONFIDENTIAL

STUDY DRUG: Orteronel

SCRI INNOVATIONS STUDY NUMBER: BRE 203

DATE OF PROTOCOL: Version 3.0 30 October 2013

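### Overall survival is censored at the first recorded non-protocol therapy, so later deaths are dropped and the reported curve and median do not estimate overall survival

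*Combined protocol and SAP*

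**What the plan says.** Protocol Section 10.6.2 gives PFS and OS one paragraph each. The OS paragraph counts time from first protocol treatment to death, and otherwise to "date last known alive (censored). If a patient receives non-protocol therapy for the study indication prior to incurring an event, the earliest date of" that therapy. The sentence closes by stating that "the earliest date of non-protocol treatment recorded will be used (censored"). The PFS paragraph contains the same sentence. Both endpoints are reported as a Kaplan-Meier curve and a median with 95% CI. No OS analysis that counts deaths after later therapy is named, and no sensitivity analysis.

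The surrounding text bears on this as follows:

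- Sections 2.2 and 10.6: OS is a secondary objective and a secondary efficacy endpoint, and "Efficacy analyses will include all patients in the ITT population".
- Section 7.6.2: "After disease progression is documented, survival will be monitored every 6 months for 2 years and annually thereafter", for up to 5 years after the last enrollment.
- Sections 5 and 5.3.2: orteronel continues until progression or unacceptable toxicity, and other breast cancer treatment is barred on study apart from permitted palliative radiation.
- Section 7.5 and Appendix E: the last scheduled review of concomitant medication is the End-of-Treatment visit ("All patients will undergo the end-of-treatment assessments listed within 30 days after treatment ends"). In the column for follow-up after progression, Appendix E lists survival only.

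One smaller sentence on PFS in Section 10.6.2 also matters: "If no post-treatment tumor assessment has been performed, PFS for the patient will be censored at time zero".

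**The concern.** Stopping the clock at new therapy is a recognised option for PFS. Applied to OS, it removes the event that the endpoint is meant to count. Kaplan-Meier needs censored patients to have the same future risk of death as those still under observation. Here the trigger for censoring is the start of another therapy, which mostly follows progression, and progression predicts death.

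Two distortions act in opposite directions. Patients with a recorded next therapy leave the risk set shortly after progression, so those who remain include more patients who are still progression-free, and this pushes the curve up. Those who remain also include patients who progressed and received nothing further. If they are sicker, the curve is pushed down. The net error has no fixed sign, and a reader of the published curve could not correct for it.

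The rule also acts only on recorded dates, yet no scheduled contact after the End-of-Treatment visit collects later therapy. Two patients with the same course can be handled differently because one start date happened to reach the database.

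**Working it through.** **No plan figure to reproduce.** The documents state no expected OS, no OS event count and no OS power. The check is therefore a reading of the rule plus an illustration on assumed inputs.

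**Step 1: the rule.** For a patient with death at time D and first recorded non-protocol therapy at time S, the written rule gives:

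- S < D: time S, censored. The death is not an event.
- No recorded S before D: time D, event.

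Survival information collected under Section 7.6.2 after S cannot enter the analysis.

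**Step 2: share of deaths excluded, by hand.** Assume 5% die without progression, a fraction *u* of the rest start next therapy, and all dates are recorded. With everyone followed to death, the excluded share is 0.95 × *u*:

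- *u* = 30%: 28.5%
- *u* = 50%: 47.5%
- *u* = 70%: 66.5%
- *u* = 90%: 85.5%

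Half of all deaths are excluded when *u* = 0.50/0.95 = 53%. Ending follow-up at 60 months lowers these shares a little, because some treated patients are still alive then, and moves the half-way point to at most about 56%.

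**Step 3: effect on the median, by simulation.** There were 64 scenarios with 200,000 patients each. Every input is an assumption:

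- exponential PFS, median 2 or 3 months; 5% die without progression
- next therapy in 30, 50, 70 or 90%, starting 1 month after progression; uptake means patients who actually start, so their survival runs from therapy start
- later median survival 8, 12 or 18 months if treated and 2, 6 or 12 months if not, never longer than treated
- 60 months of follow-up for every patient

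That makes 2 × 4 × 8 = 64 combinations, with true median OS of 5.9 to 21.6 months. The Kaplan-Meier median with censoring only at 60 months was compared with the median under the written rule. Patient counts use the planned maxima in Section 5 (31 in Cohort 1, 55 in Cohort 2).

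| Uptake | Deaths excluded | Cohort 1 (28-31 deaths) | Cohort 2 (49-55 deaths) | Error in median, months |
|---|---|---|---|---|
| 30% | 26-28% | 8-9 | 14-16 | -1.3 to +0.7 |
| 50% | 44-47% | 13-15 | 23-26 | -2.5 to +1.5 |
| 70% | 63-67% | 18-21 | 32-36 | -4.6 to +3.0 |
| 90% | 84-86% | 23-26 | 41-47 | -5.6 to +6.7 |

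Both extremes occur at 90% uptake. A true median of 18.1 is reported as 12.5 (PFS median 2; later survival 18 months treated, 2 untreated). A true median of 16.7 is reported as 23.4 (PFS median 3; 12 months in both groups). In 11 of 64 scenarios the two distortions nearly cancel (under 0.5 month).

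**Step 4: incomplete recording.** If 50% of start dates are recorded, 13-43% of deaths are excluded and the error is -1.9 to +1.3 months. At 25% recorded, the figures are 6-22% and -0.8 to +0.6.

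**Step 5: other inputs.** A separate simulation used time to progression of 2 or 4 months, post-progression survival of 8 or 14 months, and 50-90% uptake. Its true medians were compared with those under the rule, both when untreated patients survived as long as treated ones and when they survived half as long. It excluded 43-81% of deaths, with errors of about -1.8 to +7.4 months. When therapy start was made independent of death, Kaplan-Meier recovered the truth (12.0 against 12 months). The fault is therefore the dependence between therapy and prognosis, not censoring as such.

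**The case against.** The case against is mainly about size.

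- **The inputs are assumed.** This stands: the documents supply neither uptake nor survival. The largest errors need 90% uptake, and the largest negative one also needs a ninefold survival contrast (18 against 2 months). In 29 of the 64 scenarios the error is below 1 month.
- **Some patients may die in the month between progression and next therapy.** If survival is counted from progression, the excluded shares fall to 25-27%, 42-45%, 61-63% and 78-81%, and the largest positive error to about +5 months. The conclusion does not change.
- **The counts assume full accrual.** Section 5 says "up to a total of 31 patients in Cohort 1", so 31 is a maximum, as is 55 for Cohort 2. At the plan's null response rates, the chance of stopping at stage one is 0.98^19 = 0.68 in Cohort 1 and 0.949^26 + 26 × 0.051 × 0.949^25 = 0.61 in Cohort 2. Fewer patients would scale the counts down, but not the shares.
- **The eCRF is not supplied.** It may hold a field for later therapy, so the absence of a row in Appendix E does not prove that dates go uncollected. If collection is complete, however, the rule excludes the most deaths.
- **OS is descriptive.** It has no test, comparator or decision rule. This limits the consequence but does not make the estimate valid.

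None of this supplies another OS analysis or overrides the sentence.

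**Conclusion.** The concern holds as stated. The sentence is in the current protocol text, nothing modifies it, and it discards deaths that the trial is set up to collect. That the censoring is informative follows from the design, since next therapy normally comes after treatment failure. What would be labelled OS is a quantity without a clear clinical meaning.

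The size is illustrative. Depending on assumed uptake and prognosis, with full recording, the rule excludes roughly a quarter to 86% of deaths, and more than half only above about 53-56% uptake. The error in the median ranges from negligible to about 6 months either way. Response rate, disease control rate and the two-stage rules are unaffected. This should be corrected before analysis, but it does not threaten the trial's primary conclusions.

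The PFS time-zero sentence needs clarification only. The paragraph already makes death an event, but does not say which rule governs a patient who dies before any post-treatment scan.

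**What to change.** In Section 10.6.2:

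1. Delete the non-protocol-therapy sentence from the OS paragraph. OS then runs from first protocol treatment to death from any cause, censored only at the date last known alive.
2. If an OS analysis censored at new therapy is still wanted, label it supplementary and collect the start date of next therapy at the follow-up contacts.
3. In the PFS paragraph, state that time-zero censoring applies only to patients without a documented event, so that a death before the first scan counts as a PFS event on the date of death.

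The cost is one deleted sentence and one added phrase, made before the analysis. The corrected OS needs no new data, because survival follow-up is already scheduled. Extra collection arises only if item 2 is adopted.
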